### **Secondary Endpoint: Total number of new or enlarging hyperintense T2-weighted brain MRI lesions at Week 24**

The number of new or enlarging T2 hyperintense lesions at Week 24 will be analyzed using the stratified Wilcoxon-Mann-Whitney test, stratified by presence of GdE lesions at baseline (absent or present). A sensitivity analysis will be using a negative binomial regression model, adjusted for the presence of GdE lesions at baseline and region. Missing new or enlarging T2 data values will be imputed using the mean from subjects of the same treatment group at the same visit.

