8.1.2. Secondary Study Objectives

Part A

- To assess the proportion of patients who are free of GdE lesions at Week 24
- To assess the effect of RPC1063 on the cumulative number of new/enlarging T2 lesions from Week 12 to Week 24
- To compare the clinical efficacy of RPC1063 to placebo in patients with RMS as assessed by reduction in annualized relapse rate (ARR) and proportion of relapse free patients at Week 24
- To assess the safety and tolerability of RPC1063 in patients with RMS
- To assess the pharmacokinetics (PK) and PD of RPC1063 in patients with RMS

Part B

- To assess the effect of RPC1063 on the proportion of patients with new/enlarging T2 lesions at Month 24
- To evaluate whether the efficacy of RPC1063 is superior to IFN β -1a in delaying the accumulation of disability, as assessed by the Multiple Sclerosis Functional Composite (MSFC), and visual function as measured by the low contrast visual acuity test (LCLA) (Balcer, 2000).
- To evaluate whether the efficacy of RPC1063 is superior to IFN β -1a in delaying the accumulation of disability, as assessed by the Expanded Disability Status Scale (EDSS)
- To assess the effect of RPC1063 on brain atrophy over 24 months
- To evaluate the effect of RPC1063 on patient-reported quality of life as assessed by the Multiple Sclerosis Quality of Life-54 (MSQOL-54)
- To assess the safety and tolerability of RPC1063 in patients with RMS

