9. INVESTIGATIONAL PLAN

9.1. Overall Study Design and Plan

Study RPC01-201 is a multi-center, randomized, double-blind, placebo-controlled (Part A) and double-blind, double-dummy, active-controlled (Part B) parallel group study to evaluate the efficacy and safety of RPC1063 administered orally to patients with RMS.

In Part A of the study, two doses of RPC1063 will be administered daily for 24 weeks with an efficacy and safety comparison to a placebo control. This will be followed by Part B of the study, where two doses of RPC1063 will be administered daily for a 24 month period compared to an active control, IFN β -1a.

An interim analysis of Part A will be completed approximately 1 month prior to completion of Part A enrollment. Part B will commence after a DMC reviews the interim analysis data and performs a thorough safety review. Patients dosed in Part A will be ineligible for participation in Part B.

It is anticipated that the study will be performed at approximately 100-125 sites for Part A and for Part B in North America and Europe.

The study designs for Part A and Part B are shown in [Figure 1](#).

Tests and assessments are outlined in [Table 1](#) and [Table 2](#) (Part A), [Table 3](#) and [Table 4](#) (Part B), and [Table 5](#) (cardiac monitoring during dose titration), additional details regarding procedures are included in [Section 10](#). Assessments are described in [Section 11](#).

Part A

Part A is a randomized, double-blind comparison of RPC1063 to a placebo control in patients with RMS, per revised 2010 McDonald criteria ([McDonald, 2010](#); [Polman, 2011](#)).

Approximately 210 patients who meet eligibility criteria as assessed during the 30-day screening period will be randomly assigned 1:1:1 to receive one of the three following regimens, up to Week 24:

- Placebo oral capsule daily
- 0.5 mg RPC1063 oral capsule daily
- 1 mg RPC1063 oral capsule daily

The randomization will be stratified by country.

Brain MRI scans will be performed at Week 0, Week 8, and every 4 weeks thereafter, up to Week 24. Patients will be evaluated for relapses throughout the study.

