13.6.4. Efficacy

Part A

For the primary analysis, the cumulative number of GdE lesions from Week 12 to Week 24 will be compared between the 1 mg RPC1063 group and the placebo group using the stratified Wilcoxon-Mann-Whitney test, stratified by presence of GdE lesions at baseline (absent or present). This comparison will be assessed using a 2-sided test at the $\alpha=0.04944$ level of significance (to keep the overall Part A level of significant at $\alpha=0.05$, accounting for the O'Brien-Fleming adjustment and interim analysis) (Reboussin, 2000). If the comparison between the 1 mg RPC1063 group and placebo is statistically significant, then a second primary analysis will similarly compare the 0.5 mg RPC1063 group and the placebo group, also based on a 2-sided test at the $\alpha=0.04944$ level of significance. Sensitivity and descriptive analyses will also be presented.

The secondary endpoint of the proportion of patients free of GdE lesions at Week 24 will be analyzed using a logistic regression model with treatment group (three levels) and presence of baseline GdE lesions (absent, present) as factors. Pairwise comparisons between the 1 mg RPC1063 group and placebo, and between the 0.5 mg RPC1063 group and placebo, will be tested.

Quantitative endpoints such as the percent brain volume change over 24 weeks will be analyzed using analysis of covariance models with treatment group as a factor and the baseline value of the corresponding parameter as a covariate.

Endpoints that are defined in terms of lesion counts will be analyzed using the Wilcoxon-Mann-Whitney test. These analyses will include only the two groups being compared.

All secondary endpoints will be analyzed using 2-sided tests at the 5% level of significance.

Part B

The primary analysis for the ARR will be carried out using a Poisson regression model. The model will compare treatment groups, adjusted for region, age, and the number of GdE lesions at baseline. To account for multiple comparisons, each of the 2 treatment comparisons with IFN β -1a will be tested at the $\alpha = 0.025$ level. Results will be summarized by randomized treatment group and expressed as unadjusted and adjusted relapse rates, odds ratios, corresponding 95% confidence intervals, and p-values.

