#### *Analysis method*

The total number of GdE lesions from Week 12 to Week 24 will be compared between each RPC1063 group and the placebo group using the stratified Wilcoxon-Mann-Whitney test, stratified by presence of GdE lesions at baseline (absent or present). This comparison will be assessed using a 2-sided test at the alpha=0.04944 level of significance (to keep the overall Part A level of significant at alpha=0.05, accounting for the O'Brien-Fleming adjustment and interim analysis) (Reboussin, 2000).

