#### **9.2 Key Secondary Efficacy Endpoints**

The key secondary efficacy endpoints of Part A are:

- The number of GdE lesions at Week 24
- Total number of new or enlarging hyperintense T2-weighted brain MRI lesions from Week 12 to Week 24
- ARR at the end of Week 24

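### SAP 9.2.1 tests new or enlarging T2 lesions at Week 24, but the second-ranked Part A key secondary endpoint is the Week 12 to Week 24 total

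*SAP*

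**What the plan says.** **Definition.** SAP 9.2 lists the endpoint as "Total number of new or enlarging hyperintense T2-weighted brain MRI lesions from Week 12 to Week 24". SAP 4.2 and protocol 8.2.1 give the same window. The objective in protocol 8.1.2, repeated in SAP 3, is "To assess the effect of RPC1063 on the cumulative number of new/enlarging T2 lesions from Week 12 to Week 24".

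**Analysis.** SAP 9.2.1 heads the paragraph "Total number of new or enlarging hyperintense T2-weighted brain MRI lesions at Week 24" and opens it with "The number of new or enlarging T2 hyperintense lesions at Week 24 will be analyzed". The test is the stratified Wilcoxon-Mann-Whitney test, with a negative binomial model as sensitivity analysis. On missing data it says: "Missing new or enlarging T2 data values will be imputed using the mean from subjects of the same treatment group at the same visit". Protocol 13.6.4 assigns the Wilcoxon-Mann-Whitney test to lesion-count endpoints in general but does not restate the T2 variable. SAP 9.2.1 is therefore the only text specific to this analysis.

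**Schedule.** Protocol 9.1: "Brain MRI scans will be performed at Week 0, Week 8, and every 4 weeks thereafter, up to Week 24".

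**Sequence.** SAP 5 tests the secondary endpoints in rank order, 1 mg before 0.5 mg within each. T2 is second and ARR third.

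**The concern.** An analyst who programs from SAP 9.2.1 builds a Week 24 variable. One who programs from SAP 9.2 builds a Week 12 to Week 24 total. Both can point to the plan. This is a ranked step of a sequential procedure, so if the two variables gave different answers, both the T2 claim and access to the ARR test would depend on which paragraph was followed. A SAP should close that choice before unblinding. A single-visit count may also carry less information than a total over four scans, but whether it does here depends on things that the documents leave open.

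**Working it through.** **1. Scans in the window.** From the schedule in protocol 9.1, the scans from Week 12 to Week 24 are Weeks 12, 16, 20 and 24, four in all. Using one leaves 4 − 1 = 3 unused.

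**2. How the SAP words windows and single visits.**
- The primary analysis (SAP 9.1.1) tests a windowed total and writes the window out.
- The first-ranked secondary endpoint, GdE lesions at Week 24, is a true single-visit count. Its paragraph in SAP 9.2.1 has the same sentence form as the T2 paragraph.
- The T2 heading keeps the word total, but the operative sentence drops it.
- The missing-data rule works visit by visit. It fits either variable and contains no summing step.

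Read literally, the T2 paragraph describes a Week 24 count.

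**3. What a Week 24 count would contain.** No visible text names the reference scan. The central MRI manual cited in protocol 9.1.2.1 may do so.

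| Week 24 scan read against | Lesion formation covered |
|---|---|
| Week 20 | last interval only |
| Week 12 | last three intervals; omits lesions new on the Week 12 scan |
| Week 8 | all four intervals; close to the four-scan sum |
| Baseline | all four, plus lesions formed before Week 8 |

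Only the first row discards most of the window.

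**4. The plan's own power figure, which is for the primary GdE endpoint.** Inputs from SAP 5.1: P = 0.65, 80% power, 59 per group, 15% dropout. Noether's formula with equal groups is

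N = (z₁₋α/₂ + z₁₋β)² / [12 × 0.25 × (P − 0.5)²].

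At two-sided α = 0.05, N = 116.28, or 58.14 per group, rounded up to 59. At the primary level ("This comparison will be assessed using a 2-sided test at the alpha=0.04944 level of significance"), it is 58.34 per group, again 59. With dropout, 59 / 0.85 = 69.4, so 70 per arm and 210 in total. The stated figures reproduce. Neither document gives an effect size or power for T2.

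**5. Illustration for the Week 20 reference.** Everything about lesion counts here is assumed. Each patient has four scan counts, Poisson with mean m × [w·s + (1 − w)·g]. Here s is a patient effect shared across scans and g is a scan-specific effect; both are gamma with mean 1 and variance d. The active rate ratio was chosen so that the four-scan total has P ≈ 0.65, a value borrowed from the GdE endpoint. There were 59 patients per arm and 3,000 replicates, with a tie-corrected unstratified Wilcoxon test. The level was two-sided 0.05, following protocol 13.6.4 ("All secondary endpoints will be analyzed using 2-sided tests at the 5% level of significance").

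| w | m | d | P, Week 24 | Power, total | Power, Week 24 | Loss (points) |
|---|---|---|---|---|---|---|
| 1.0 | 0.3 | 2 | 0.576 | 94.8% | 71.5% | 23.3 |
| 1.0 | 0.3 | 4 | 0.581 | 98.9% | 90.4% | 8.5 |
| 1.0 | 1.0 | 2 | 0.613 | 85.7% | 74.1% | 11.6 |
| 1.0 | 1.0 | 4 | 0.618 | 91.4% | 87.5% | 3.9 |
| 1.0 | 2.0 | 2 | 0.629 | 83.1% | 76.8% | 6.3 |
| 1.0 | 2.0 | 4 | 0.630 | 86.2% | 87.3% | −1.1 |
| 0.7 | 0.3 | 2 | 0.567 | 89.8% | 50.9% | 38.9 |
| 0.7 | 0.3 | 4 | 0.568 | 92.2% | 59.5% | 32.7 |
| 0.7 | 1.0 | 2 | 0.591 | 82.1% | 49.3% | 32.8 |
| 0.7 | 1.0 | 4 | 0.589 | 84.2% | 52.6% | 31.6 |
| 0.7 | 2.0 | 2 | 0.605 | 82.3% | 54.4% | 27.9 |
| 0.7 | 2.0 | 4 | 0.598 | 83.7% | 53.2% | 30.5 |

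The standard error of each power is at most √(0.25/3000) = 0.9 points, so the −1.1 is best read as no loss. The loss is small when a patient's activity is fully shared across scans and large when it varies from scan to scan.

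**The case against.** The strongest reply is that this is a drafting slip. The heading still says total, SAP 9.2 restates the window directly above, and SAP 5 takes the rank order from protocol 8.2, where the window is also stated. SAP 2 asks for the plan to be read with the protocol. The documents also label accumulated quantities by their end point elsewhere: SAP 5.1 and protocol 13.2 describe the primary comparison as a cumulative count at the end of Week 24. All of this stands, and a slip is plausible. It does not remove the need for correction, because the slip sits in the only paragraph that specifies the analysis.

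A reader might go further and infer that three of four scans are dropped and that power falls from a planned level. The documents do not support that. The scan loss needs a Week 20 reference, which is nowhere stated. No power is planned for this endpoint, so there is no level to fall from, and P = 0.65 belongs to the GdE primary endpoint. The simulated test is also unstratified, whereas SAP 9.2.1 stratifies. Nor is the ARR consequence peculiar to the Week 24 variable: a failed T2 step would close the ARR step under either definition.

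It is also fair to object that summing four scans is incomplete as a remedy. If every scan were read against baseline, the sum would count a persisting lesion at each visit. The fix therefore has to name the reference scan.

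**Conclusion.** The mismatch is established from the text alone: the ranked endpoint is a Week 12 to Week 24 total, and the analysis paragraph specifies a Week 24 count. The protocol version in hand (4.0, October 2014) is later than the SAP (V1.2, May 2014) and keeps the window, so no later redefinition in the protocol explains it. The paragraph should be corrected because it governs a confirmatory step ahead of ARR. The Part A primary analysis is not affected.

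The size of the consequence is not established. It ranges from close to nothing, if Week 24 is read against Week 8, to a probable loss of power if it is read only against Week 20. For that last case the simulations give 82% to 99% power for the total and 49% to 90% for Week 24 alone. Those figures rest wholly on the assumed lesion rates, dispersion, between-scan correlation and borrowed effect size.

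**What to change.** In SAP 9.2.1:

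1. Change the heading and first sentence to the total number of new or enlarging T2 lesions from Week 12 to Week 24, defined as the sum over the Week 12, 16, 20 and 24 scans.
2. State that each scan is read against the preceding scan (Week 12 against Week 8, and so on), so that a persisting lesion is not counted again. Say which scan is used when the preceding one is missing, and check that this agrees with the MRI manual.
3. Apply the by-visit imputation to each scan before summing.
4. Apply the stratified Wilcoxon-Mann-Whitney test and the negative binomial sensitivity model to that sum.

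The Week 24 count can stay as a descriptive by-visit summary. The cost is a few lines of SAP text, settled before unblinding, and confirmation of the reading rule with the central reading facility. All four scans, and the Week 8 reference, are already scheduled.

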### **Secondary Endpoint: ARR at the end of Week 24**

#### *Definition of relapses*

The relapse rate will be based on only relapses that were determined by the treating investigator to meet the protocol-defined definition of relapse, based on the EDSS scores obtained by the blinded evaluator ([Section 9.1.2.3](#) in Protocol). New or recurrent neurological symptoms that occur less than 30 days following the onset of a protocol-defined relapse will be considered part of the same relapse, i.e., if 2 relapses have onset days that are <30 days of one another, they will be counted as 1 relapse.

#### *Definition of relapse rate*

The relapse rate for each treatment group will be calculated as the total number of relapses experienced in the group divided by the total number of days in the study for the group, and multiplied by 365. This is called the unadjusted relapse rate.

#### *Analysis method – annualized relapse rate*

## 16.1.9 Documentation of Statistical Methods

Receptos, Inc.  
Protocol RPC01-201

Statistical Analysis Plan – Part A, V1.2  
Date Issued: May 20, 2014

ARR at the end of Week 24 will be analyzed using a Poisson regression model. The model will compare treatment groups, adjusted for region, the number of relapses within 24 months prior to the study, and presence of GdE lesions. A sensitivity analysis will be using a negative binomial regression model to compare ARR with the same covariates as specified for the Poisson model.

### 9.3 Exploratory Efficacy Endpoint

The exploratory endpoints of Part A are:

#### 9.3.1 Analysis

**Exploratory Endpoint:**

**Exploratory Endpoint:**

### 16.1.9 Documentation of Statistical Methods

Receptos, Inc.  
Protocol RPC01-201

Statistical Analysis Plan – Part A, V1.2  
Date Issued: May 20, 2014

CELGENE PROPRIETARY INFORMATION

### 16.1.9 Documentation of Statistical Methods

Receptos, Inc.  
Protocol RPC01-201

Statistical Analysis Plan – Part A, V1.2  
Date Issued: May 20, 2014

CELGENE PROPRIETARY INFORMATION

### 16.1.9 Documentation of Statistical Methods

Receptos, Inc.  
Protocol RPC01-201

Statistical Analysis Plan – Part A, V1.2  
Date Issued: May 20, 2014

[REDACTED]

## 10 Safety Analysis

All analysis of safety will be conducted using the Safety population. Statistical hypothesis testing will not be performed on any safety results.

### 10.1 Adverse Events

A treatment emergent AE is any reaction, side effect, or other untoward event, regardless of relationship to study drug, which occurs any time after the first dosing of study drug, until 28 days following the last dose of treatment with the study drug. During the study, clinically significant adverse changes in clinical status, ECGs, and physical examinations are considered AEs. Any patient complaints associated with such an abnormal finding will also be reported as an AE.

## 16.1.9 Documentation of Statistical Methods

Receptos, Inc.  
Protocol RPC01-201

Statistical Analysis Plan – Part A, V1.2  
Date Issued: May 20, 2014

Adverse events include, but are not limited to: (1) a worsening or change in nature, severity, or frequency of conditions present at the start of the study; (2) patient deterioration due to primary illness; (3) intercurrent illness; and (4) drug interaction.

An abnormal laboratory value will only be reported as an AE if it involves therapeutic medical intervention, if the Investigator considers it to be an AE, or if it leads to study discontinuation.

A treatment emergent AE is defined as an AE that meets any of the following conditions:

- begins on or after Study Day 1;
- begins before Study Day 1 and worsens in severity after Study Day 1.

Adverse events with unknown onset dates or unknown end dates will be counted as having occurred during the study treatment period unless the event resolves before Study Day 1. Adverse events with unknown severity will be counted as severe. Adverse events with unknown relationship to study drug will be counted as probably related to study drug.

Only treatment-emergent AEs will be presented, according to the Medical Dictionary for Regulatory Activities (MedDRA®), system organ class (SOC), and preferred term (PT).

### 10.1.1 Incidence of Adverse Events

The incidence of AE table will include only one occurrence of a preferred term per patient. If a subject reports the same preferred term multiple times, then that preferred term will only be incremented by one since patient counts will be presented. As with the preferred term, if a patient reports multiple AEs within the same body system, then that body system will only be incremented by one since patient counts will be presented. For tables showing incidence by SOC and PT, PTs will be sorted within SOC in descending order of incidence in the RPC1063 1 mg group. For tables showing incidence by PT only, the PTs will be sorted in descending incidence in the RPC1063 1 mg group.

The incidence of all treatment-emergent AEs will be presented by SOC and PT and separately by PT only.

All AEs will be presented in a listing.

### 10.1.2 Relationship of Adverse Events to Investigational Product

A summary of AEs by relationship to study drug will be presented in a table by incidence of occurrence. The relationships will be collected as the possibility that study drug caused the event. The possible relationships are “Unrelated”, “Unlikely”, “Possible”, “Probable” and “Related”. A treatment-related AE is an AE with any relation to study drug other than “Unrelated” or “Unlikely”. In the AE relationship table, if a subject reports multiple occurrences of the same AE, only the most closely related occurrence

## 16.1.9 Documentation of Statistical Methods

Receptos, Inc.  
Protocol RPC01-201

Statistical Analysis Plan – Part A, V1.2  
Date Issued: May 20, 2014

will be presented. Adverse events (AE) that are missing relationship will be presented in the summary table as “Probable” but will be presented in the data listing with a missing relationship.

### 10.1.3 Severity of Adverse Event

A summary of AEs by severity will be presented in a table. Adverse events will be classified by severity (mild, moderate and severe). In the AE severity table, if a subject reported multiple occurrences of the same AE, only the most severe will be presented. Adverse events (AE) that are missing severity will be presented on tables as “Severe” but will be presented in the data listing with a missing severity.

### 10.1.4 Serious Adverse Events

The seriousness of an AE should be assessed by the Investigator independently from the severity of the AE. A serious adverse event (SAE) is defined as any untoward medical occurrence that at any dose results in death, is life-threatening, requires inpatient hospitalization or prolongation of existing inpatient hospitalization, or results in significant disability/incapacity.

Important medical events that may not result in death, be life-threatening, or require hospitalization may be considered SAEs when, based upon medical judgment, they may jeopardize the subject and may require medical or surgical intervention to prevent one of the outcomes listed above.

The incidence of SAEs will be presented in a table. The incidence of treatment-related SAEs will also be presented in a table. A treatment-related SAE is a SAE with any relation to study drug other than “Unrelated” or “Unlikely”. The table of SAEs will include only one occurrence of a preferred term per patient. If a subject reports the same SAE preferred term multiple times, then that preferred term will only be incremented by one since subject counts will be presented. As with the preferred term, if a subject reports multiple SAEs within the same body system, then that body system will only be incremented by one since subject counts will be presented. Incidences of SAEs will be presented by SOC and PT. SAEs will also be listed separately.

### 10.1.5 Adverse Events Leading to Treatment Discontinuation

All AEs collected with an investigational product action taken as “Permanently discontinued” will be summarized in a table and presented in a listing.

